## 2.3 Rationale

## 2.3.1 Rationale for the Dose Selection

The starting dose of VP-315 for this study was selected based on IND-directed toxicity studies and on experience gained from previous clinical studies of LTX-315 in adults with solid tumors. Although no NOAEL could be determined in toxicology studies due to the pharmacological action of the compound, these studies have generated data which assist in the selection of a tolerable clinical starting dose.

In the Phase 1 monotherapy dose-escalation study (C08-315-01), 14 subjects received injections of intratumoral LTX-315 at doses ranging from 1.4 mg to 9.0 mg on Day 1. Grade 2 AEs were not noted at doses below 4.0 mg on Day 1, a determinative factor in the proposed LTX-315 starting total daily dose of 2.0 mg in the current study. Additionally, BCC lesions are expected to be less vascularized than the malignancies injected to date, which is also expected to further reduce systemic effects.

In C08-315-01, at LTX-315 doses below 4.0 mg, the AEs occurring on Day 1 had a short duration (minutes), and at all doses became less severe and of shorter duration with additional LTX-315 exposure. Similarly, preclinical testing (IV administration in rats) indicates that LTX-315–related hypotension is a result of a direct effect on peripheral vasculature (without any central cardiac effect) and exhibits a tachyphylaxis effect (i.e., the largest reduction in BP occurs following the first LTX-315 dose; subsequent identical LTX-315 doses resulted in diminished BP reductions). For these reasons, the proposed total daily dose of VP-315 will be administered in 2 injections, with the initial 30% (150  $\mu$ L) of the VP-315 dose being administered in the first injection, and the remaining 70% (350  $\mu$ L) administered at least 15 minutes and no more than 30 minutes later. In all parts of the study, the targeted total volume of delivery is 500  $\mu$ L daily. The Safety Review Committee (SRC; see Section 7.4.1) may determine in Part 2 to explore a lower volume of delivery at 250  $\mu$ L daily at doses at or below 5.0 mg delivered as 75  $\mu$ L in the first dose and 175  $\mu$ L in the second dose.

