### **3.6. Cohort 4 (N = 36 [10 initial / 26 expansion] at two times weekly dosing)**

Subjects receive VP-315 via once-daily dosing of 8 mg, administered on 2 consecutive days in one week (W1D1, W1D2). The planned dosing regimen is a split dose of VP-315 for all treatments. The 500 $\mu$ L (8 mg) dose is to be divided into 2 injections given at least 15 minutes and no more than 30 minutes apart, with 30% (150  $\mu$ L) administered in the first injection and the remaining 70% (350  $\mu$ L) with the second injection. Treatment for a second TL may begin on D1 of the next week (W2D1, W2D2). Each individual TL is treated for the assigned 2 days only (regardless of necrosis status). Up to 2 TLs may be treated – up to 4 total doses. Subjects with only 1 TL who complete week one of treatment without complete necrosis receive no additional treatment.

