### **3.7. Cohort 5 (N = 37 [10 initial / 27 expansion] at three times weekly dosing)**

Subjects receive VP-315 via once-daily dosing of 8 mg, administered on 3 consecutive days in one week (W1D1, W1D2, W1D3). The planned dosing regimen is a split dose of VP-315 for all treatments. The 500 $\mu$ L (8 mg) dose is to be divided into 2 injections given at least 15 minutes and no more than 30 minutes apart, with 30% (150  $\mu$ L) administered in the first injection and the remaining 70% (350  $\mu$ L) with the second injection. Treatment for a second TL may begin on D1 of the next week (W2D1, W2D2, W2D3). Each individual TL is treated for the assigned 3 days only (regardless of necrosis status). Up to 2 TLs may be treated – up to 6 total doses. Subjects with only 1 TL who complete week one of treatment without complete necrosis receive no additional treatment.

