### **5.5. Definition of Baseline and Treatment Groups**

Baseline is defined as the most recent non-missing value obtained prior to first injection of study treatment. Summaries will be provided for the following groups, unless limited to a subset of these groups elsewhere in this SAP:

- Part 1
- Part 2
  - Cohort 1
  - Cohort 2
  - Cohort 4
  - Cohort 4 Expansion
  - Cohort 5
  - Cohort 5 Expansion
  - Overall (i.e., Part 2 Total, Displayed Total, or Expansion Total)

No other group or subgroup analyses will be performed.

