  - Severity  $\geq$  Moderate Events of Only Cutaneous Injection Site Reactions (excluding Severity = Not Applicable):
    - TEAE
    - TEAE by Strongest Relationship to Study Treatment
    - TEAE Occurring upon Study Treatment through Observation Period
    - TEAE with Local Reactogenicity (Injection site erythema, Injection site induration)
  - Serious TEAE
  - DLT - Part 1 Only
  - TRAE SI - Part 2 Only
  - TEAE Leading to Study Treatment Discontinuation

Verrica Pharmaceuticals Inc.  
Protocol: VP-315-201

Statistical Analysis Plan  
6-Sep-2024

- TEAE Leading to Study Discontinuation
- TEAE Leading to Death

Categories for Relationship to Study Treatment are Related and Not Related, and categories for Severity are Mild, Moderate, and Severe where the severe category will include severity levels of severe, life-threatening, and fatal as applicable.

Summaries of DLT events, TRAE SI events, and TEAEs for a subject Occurring upon Study Treatment through its Observation Period (e.g. during the DLT observation period or TRAE SI observation period) are TEAEs that a subject experiences on any day on which treatment occurs. This definition of the DLT and TRAE SI observation periods deviates from the protocol as described in section 14.

In addition, for each of the nineteen listed item mentioned previously in this section of the SAP, summaries for the total number of TEAEs, the number and percentage of subjects with at least one TEAE, and the number and percentage of subjects with at least one TEAE categorized by system organ class (SOC) and PT will be provided. Subjects having more than one AE may appear in more than one SOC or PT but will be counted at most once per each SOC and PT. For maximum severity, subjects will be counted at the most extreme category among the mild, moderate, and severe categories. For relationship to study treatment, subjects will be counted at the most related category among the unrelated and related categories. SOC and PT will be displayed in order of decreasing frequency of total SOC count, followed by decreasing frequency of total PT count, and then alphabetically if tied.

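### TRAE and TRAE SI percentages in Cohorts 4 and 5 mix the 2-day v 3-day regimen with the share of two-lesion subjects; a Week 1 row would separate them

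*SAP*

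**What the plan says.** SAP 9.1 works on the Safety Population. For every listed item, TRAEs and TRAE SIs among them, "the number and percentage of subjects with at least one TEAE categorized by system organ class (SOC) and PT will be provided", together with the total number of events. The Part 2 columns come from SAP 5.5: Cohorts 1 and 2, Cohorts 4 and 5 with their expansion groups shown separately, and an overall column. No adverse event table has rows for treatment week, dosing day or lesion. SAP 9.1 and 14 restrict TRAE SIs to days on which treatment occurs.

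Dosing is defined per lesion: two days in Cohort 4 (SAP 3.6) and three in Cohort 5 (SAP 3.7), necrosed or not. For Cohort 4, "Up to 2 TLs may be treated – up to 4 total doses"; for Cohort 5, "Up to 2 TLs may be treated – up to 6 total doses". A second lesion starts in Week 2 at the earliest. In both cohorts, "Subjects with only 1 TL who complete week one of treatment without complete necrosis receive no additional treatment". SAP 8 notes that every subject has a first target lesion but not all have more.

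Enrolment is sequential and open-label (Protocol 7.1), and SAP 5.4 plans no covariate analysis. The primary objective for these cohorts is safety, tolerability and dosing-regimen information for a pivotal design (SAP 2).

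**The concern.** Cohorts 4 and 5 differ by design in dosing days per lesion, 2 v 3. The planned percentage is per subject over the whole study, and a subject's exposure also depends on lesion count. A two-lesion Cohort 4 subject has 4 planned dosing days (4 × 8 = 32 mg); a one-lesion Cohort 5 subject has 3 (3 × 8 = 24 mg). On this measure the shorter regimen can carry the larger exposure.

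For TRAE SIs the link is direct, because the days on which one can be counted are the dosing days, so a second lesion doubles the planned window. If two-lesion subjects are more common in one cohort, the tables can enlarge, shrink or reverse the contrast that someone planning the pivotal regimen would look for.

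**Working it through.** **Plan's own figures.** Days per lesion × lesions: Cohort 4, 2 × 1 = 2 and 2 × 2 = 4; Cohort 5, 3 × 1 = 3 and 3 × 2 = 6. The maxima of 4 and 6 in SAP 3.6 and 3.7 are reproduced. Cohort sizes: 10 + 26 = 36 and 10 + 27 = 37, as stated. Protocol 7.3.2.2 lists only two Week 2 days for the second Cohort 5 lesion yet still gives 6 total doses. The Protocol synopsis, Protocol 4.1, Table 7-1 and SAP 3.7 list three. These passages must be reconciled; 6 is used here.

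**Assumptions, not in the documents.** Risk q of a TRAE SI per dosing day, equal in both cohorts and independent between days; two-lesion shares f4 and f5.

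**Formulas.** P(k) = 1 − (1 − q)^k for k dosing days. Cohort 4 rate = (1 − f4)·P(2) + f4·P(4). Cohort 5 rate = (1 − f5)·P(3) + f5·P(6). Stopping after a first TRAE SI does not change the chance of having at least one, so these hold even if dosing stops there.

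**At q = 10%.** P(2) = 1 − 0.9² = 19.0%; P(3) = 27.1%; P(4) = 34.4%; P(6) = 46.9%.

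| Two-lesion share, C4 / C5 | Cohort 4 | Cohort 5 | Gap (points) |
|---|---|---|---|
| 40% / 40% | 0.6 × 19.0 + 0.4 × 34.4 = 25.2% | 0.6 × 27.1 + 0.4 × 46.9 = 35.0% | 9.8 |
| 60% / 20% | 0.4 × 19.0 + 0.6 × 34.4 = 28.2% | 0.8 × 27.1 + 0.2 × 46.9 = 31.1% | 2.8 |
| 20% / 60% | 0.8 × 19.0 + 0.2 × 34.4 = 22.1% | 0.4 × 27.1 + 0.6 × 46.9 = 39.0% | 16.9 |
| Week 1 only, any mix | 19.0% | 27.1% | 8.1 |

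Gaps are taken before rounding; the rounded rates in the second row subtract to 2.9.

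**Sensitivity to q.** At q = 5% the same rows give 13.3% v 19.2% (5.9), 15.0% v 16.7% (1.7), 11.5% v 21.6% (10.1) and, for Week 1, 9.8% v 14.3% (4.5). At q = 2% the gaps are 2.6, 0.7, 4.5 and 1.9 points.

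**Where the contrast vanishes.** At q = 10%, shares of 80% v 20% give 31.3% v 31.1%, essentially no gap although the regimens differ by a day per lesion. At the limit of all v none, Cohort 4 is higher, 34.4% v 27.1%.

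**Constant risk is a simplification.** Protocol 2.3.1 reports, from intravenous dosing in rats, that "the largest reduction in BP occurs following the first LTX-315 dose", and that in an earlier study of the drug adverse events became milder and shorter with further exposure. If risk falls with repeated dosing, second-lesion days add less than shown and the lesion-mix effect is smaller. The Week 1 contrast remains 2 v 3 planned days for everyone.

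**The case against.** The strongest reply is that much of the safety picture is already broken down. SAP 7.1.2 reports treatment discontinuation, with adverse event as a reason, separately for the first and second target lesion. SAP 9.5 gives the cutaneous reaction assessment, itself a primary endpoint, by visit within lesion. SAP 9.3 counts hypotension-threshold events by injection visit. A reader might infer that every primary safety endpoint is blurred by lesion count; the documents do not support that. The point is confined to TRAEs and TRAE SIs in SAP 9.1. Their other components, such as Grade 2 injection-site pain, headache or fever, have no such breakdown there.

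A reader might also take SAP 5.5, "No other group or subgroup analyses will be performed", as forbidding the remedy. It limits groups of subjects. Rows by visit or lesion appear throughout the SAP, and a Week 1 row covers every treated subject.

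It is also fair that the lesion shares are invented, that both cohorts have the same eligibility rules, and that with equal 40% shares the 9.8-point gap reflects the regimens' different numbers of dosing days. The two unequal mixes move it by about 7 points either way. With 36 and 37 subjects and rates near 30%, the standard error of the difference is √(0.3 × 0.7 × (1/36 + 1/37)) ≈ 10.7 points, so the distortion is smaller than sampling error. That limits its weight but does not excuse it, because this component can be removed at little cost.

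Finally, SAP 7.1.2 and 7.6 show second-lesion treatment and dosing by visit, and the adverse event listing carries start dates. A reader could rebuild a Week 1 count from the listings, but no planned table gives it.

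**Conclusion.** The point holds for TRAEs and TRAE SIs. Their per-subject percentages in Cohorts 4 and 5 combine a 2-day v 3-day regimen with the share of subjects treated for a second lesion, and no planned table in SAP 9.1 separates the two. Under the stated assumption of 10% per dosing day, lesion mix alone moves the apparent gap from about 3 to about 17 points around 9.8.

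These figures illustrate sensitivity; they do not estimate bias in this trial. Nothing in the documents shows that the lesion mix differed between cohorts, only that sequential enrolment does not balance it. The study is descriptive with no hypothesis test, so no error rate is affected. This is an inexpensive improvement to how the regimens are described, made worthwhile by the cohorts' stated purpose.

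**What to change.** In SAP 9.1, for Cohorts 4 and 5 and their expansion groups:

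- Add the number and percentage of subjects with a TRAE, and separately with a TRAE SI, starting from W1D1 up to but not including W2D1. Use all treated subjects as the denominator. Only the first lesion is dosed in that window, so the contrast is 2 v 3 planned dosing days for everyone. Where a one-lesion subject has no W2D1 visit, state the calendar day that closes the window; the Protocol's 7-day treatment week makes that Day 8.
- Show the number of one-lesion and two-lesion subjects per cohort beside the whole-study rows, which stay as planned.
- If a Week 2 row is added, label it as limited to subjects who went on to a second lesion. They are a selected group: under Protocol 10.2 and SAP 5.9 a TRAE SI ends dosing, and Cohort 5 has one more Week 1 day on which that can happen.

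The cost is a few table rows from adverse event start dates and injection dates already collected. Rows specified before database lock remain a priori under SAP 5.2; later ones must be labelled post hoc. The downside is that Week 1 counts are smaller and omit reactions that start later, which is why the whole-study rows should stay.

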## 9.2. Clinical Laboratories

Summaries of (a) serum chemistry, (b) hematology, and (c) serum tryptase will be provided using descriptive statistics and the safety population. Any clinically significant post-baseline laboratory result is to be collected as an adverse event and included in the summary of adverse events.

Verrica Pharmaceuticals Inc.  
Protocol: VP-315-201

Statistical Analysis Plan  
6-Sep-2024

Results for serum tryptase and for the following laboratory parameters are expected to be available for summarization using the International System of Units (i.e., standard units).

Serum Chemistry	Hematology

 
• Albumin
 
• Alkaline Phosphatase (ALP)
 
• Alanine Aminotransferase (ALT) (Serum Glutamic Pyruvic Transaminase (SGPT))
 
• Aspartate Aminotransferase (AST) (Serum Glutamic Oxaloacetic Transaminase (SGOT))
 
• Blood Urea Nitrogen (BUN)
 
• Bicarbonate
 
• Calcium
 
• Chloride
 
• Creatinine
 
• Glucose
 
• Lactic Dehydrogenase (LDH)
 
• Potassium
 
• Sodium
 
• Total Bilirubin
 
• Total Protein
 
	
 
• Hematocrit
 
• Hemoglobin
 
• Mean Corpuscular Hemoglobin Concentration (MCHC)
 
• Mean Corpuscular Volume (MCV)
 
• Platelet Count
 
• Red Blood Cell Count (RBC)
 
• White Blood Cell Count (WBC) with Differential (Absolute) 
 
○ Bands
 
○ Blasts
 
○ Basophils
 
○ Eosinophils
 
○ Lymphocytes
 
○ Monocytes
 
○ Neutrophils
 
 
 

Serum chemistry and hematology summaries will present scheduled visit and include baseline (Screening, Baseline, W1 Safety Assessment, W2 Safety Assessment, EOS 1 Week Post-excision, EOS 2 Weeks Post-excision) within alphabetically ordered laboratory parameters and, for continuous parameters, include descriptive statistics for baseline and change from baseline for post-baseline visits, if possible.

The serum tryptase summary will present scheduled visit and include baseline (Screening, Baseline, W1D1, W1D2, W1D3, W2D1, W2D2, W2D3 – not all labs are collected at all scheduled visits) and include descriptive statistics for baseline and change from baseline for post-baseline visits without timepoints, if possible. If timepoint measurements occur, serum tryptase will be displayed by scheduled timepoint (Immediately after Hypersensitivity Reaction, 60-120 min after Hypersensitivity Reaction) within scheduled post-baseline visit and include (a) descriptive statistics for

baseline and change from baseline for post-baseline timepoints, if possible, and (b) the number and percent of subjects with at least one significant elevation, where significant elevation of serum tryptase is defined as a post-baseline value  $\geq (1.2 \times \text{baseline value}) + 2$ .

Shift tables for laboratory parameters previously listed in this section of the SAP for (a) serum chemistry and (b) hematology will be presented, if possible, at each scheduled post-baseline visit using the safety population. Abnormal/out of range laboratory values are to be flagged as either Low or High. As CTCAE grading is not provided for numerous laboratory data, shift tables to assess changes from baseline will be presented using Low, Normal, High, and Total as categories.

Separate listing will be provided for serum chemistry, hematology, and serum tryptase using the safety population, and these lab listings will include whether Collection was Performed (Yes, No), Visit, Date and Time of Collection, Result and Units using the International System of Units (i.e., standard units), Lower and Upper Reference Range Limits using the International System of Units, Reference Range Indicator (Low, Normal, High), if available, CTCAE grade, if available, Clinical Significance (NCS, CS) for abnormal results, if available, and Change from Baseline using the International System of Units. The serum tryptase listing will also include the following for post-baseline results:

- Did the subject have a hypersensitivity reaction?
- Was a blood sample collected immediately after the hypersensitivity reaction for the serum tryptase assessment collected?
- Was the second blood sample collected between 60 - 120 minutes after the hypersensitivity reaction for the serum tryptase assessment collected?

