# 11.5.2 Safety Analyses

All subjects who receive any amount of study drug will be included in the safety analysis. Safety will be evaluated by study part.

All AEs will be coded using the MedDRA dictionary. Tabular summaries of AEs will only consider treatment-emergent adverse events (TEAEs), which are defined as those AEs with a start date on or after first dose of study drug. The incidence of TEAEs will be summarized by system organ class (SOC), preferred term (PT), relationship to study drug, and severity. Serious TEAEs will be summarized by SOC and PT. TEAEs leading to discontinuation as well as TEAEs identified as dose limiting toxicities will be listed and summarized if sufficient counts of either are reported.

Hematology and serum chemistries will be summarized using conventional summary statistics (mean, standard deviation, median, and range). In addition, a change from baseline will be presented. Standard shift tables will also be prepared presenting toxicity grade vs baseline.

Vital signs and ECG results will be summarized in a descriptive manner by calculating the mean, standard deviation, median, and range in the same manner described for laboratory values. Change from baseline for vital signs and ECG parameters will also be summarized. For ECG parameters, both QTcB (Bazett's correction) and QTcF (Fridericia's correction) will be displayed.

Cutaneous Reaction Assessments will be summarized using counts and percentages for each severity level (none, mild, moderate, severe). Separate summaries will be presented for each cutaneous reaction type and visit.

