### **14. Where Statistical Analysis Plan Differs from Protocol**

The following are changes in this SAP that differ from the protocol:

- In Section 2 of this SAP, Objectives and Endpoints and Section 8.3, Estimate of Remaining Tumor Volume and Reduction in Tumor Volume at Excision:  
Estimate of reduction in tumor volume (necrotic cells:tumor cells) at excision is added as an additional endpoint not included in the protocol.
- In Section 6 of this SAP, Analysis Populations:  
A definition of enrolled subjects is not included in the protocol but is included in this SAP.
- In Section 8.3 of this SAP, Estimate of Remaining Tumor Volume at Excision:

The protocol mentions that the estimated remaining tumor volume would be necrotic cells:tumor cells. However, the estimated remaining tumor volume will be provided by the dermatopathologist and captured in EDC as an estimate of viable tumor within estimated volume of the entire tumor bed expressed as a percentage.

- In Section 9.1 of this SAP, Adverse Events:

Per protocol, the DLT observation period for Part 1 subjects is given as completing Week 1 dosing. In this SAP, to clarify that completing dosing is not necessary for observation, the DLT observation period for Part 1 subjects any day on which treatment occurs Per protocol, the TRAE SI observation period for Part 2 subjects occurs during treatment visit. In this SAP, the TRAE SI observation period for Part 2 subjects is defined as any day on which treatment occurs.

- In Section 9.2 of this SAP, Clinical Laboratories:

As CTCAE grading is not provided for numerous laboratory data, shift tables to assess changes from baseline will be presented using Low, Normal, High, and Total as categories.

- In Section 12 of this SAP, Pharmacokinetic Analysis:

Per protocol, concentrations of LTX-315 and metabolites were to be provided, but the data will contain only LTX-315 concentrations.

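### The SAP drops toxicity grade from every chemistry and hematology shift table, although its stated reason covers only part of the laboratory data

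*SAP*

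**What the plan says.** Protocol 11.5.2 (Safety Analyses) commits to graded tables for hematology and serum chemistry: "Standard shift tables will also be prepared presenting toxicity grade vs baseline". Protocol 7.4.2 names CTCAE v5.0 as the scale for grading safety events.

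SAP 9.2 (Clinical Laboratories) changes the categories. Values are classified only by the side of the reference range on which they fall, "Abnormal/out of range laboratory values are to be flagged as either Low or High", and "shift tables to assess changes from baseline will be presented using Low, Normal, High, and Total as categories". This applies to all the chemistry and hematology parameters listed there, at each scheduled post-baseline visit. Serum tryptase is outside these tables and has its own elevation threshold.

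The reason, stated in SAP 9.2 and repeated in SAP 14, is "As CTCAE grading is not provided for numerous laboratory data". SAP 14 opens its list with "The following are changes in this SAP that differ from the protocol", so the departure is declared. SAP 13 gives the SAP precedence over the protocol.

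The grade survives only in the by-subject listings of SAP 9.2. Besides the result and both reference limits, these are to show "CTCAE grade, if available, Clinical Significance (NCS, CS) for abnormal results, if available, and Change from Baseline using the International System of Units". The other tabulated view of magnitude is the visit-wise summaries, which "include descriptive statistics for baseline and change from baseline for post-baseline visits, if possible".

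**The concern.** The reason given is narrower than the change. Grades missing for *numerous* data explain why a graded table cannot be made for some parameters. They do not explain dropping it for parameters that do carry a grade, and the listing specification expects that some may.

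A shift table ties each subject's post-baseline value to that subject's own baseline and counts subjects. With only Low, Normal and High it loses all information on distance beyond the limit. A slight and a gross elevation from a normal baseline fall in the same cell, and further worsening from an abnormal baseline sits on the diagonal. Abnormal baselines are possible: exclusion criterion 5 in Protocol 5.3 removes values that the investigator judges clinically significant, not every value outside the range.

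At stake is a tabulated count of subjects with graded laboratory changes, in a study whose primary objectives concern safety and tolerability.

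**Working it through.** The plan gives no figure on this point to reproduce. The check applies the SAP's classification rule and then asks what each planned display can show.

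**Inputs**
- Rule (SAP 9.2): Low if below the lower limit, High if above the upper limit, otherwise Normal.
- Reference limits: none in the documents. Assumed, in multiples of the upper limit: lower 0.25, upper 1.00.
- Group sizes (SAP 3.2, 3.6, 3.7): 10 in each initial group of Cohorts 4 and 5; 26 and 27 in the expansion groups; 82 in Part 2.

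**Step 1. Apply the rule.**

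| Baseline | Post-baseline | Ratio | Shift table |
|---|---|---|---|
| 1.1 | 1.2 | 1.2/1.1 = 1.09 | High to High |
| 1.1 | 2.2 | 2.2/1.1 = 2.0 | High to High |
| 1.1 | 5.5 | 5.5/1.1 = 5.0 | High to High |
| 1.1 | 11 | 11/1.1 = 10.0 | High to High |
| 1.5 | 7.5 | 7.5/1.5 = 5.0 | High to High |
| 0.24 | 0.05 | 0.05/0.24 = 0.21 | Low to Low |

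All six count as no shift. From a normal baseline, a rise to 1.1 and a rise to 5.5 are both Normal to High.

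**Step 2. Does this depend on the assumed limits?** No. Any two values above the same upper limit, or below the same lower limit, share a category whatever the limit is.

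**Step 3. What do the descriptive statistics retain?** Take one subject rising from 1.1 to 5.5, a change of 5.5 − 1.1 = 4.4, with no change in the others. The mean change is 4.4/n:
- n = 10: 0.44
- n = 26: 0.17
- n = 27: 0.16
- n = 82: 0.05

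The mean dilutes the case, but SAP 5.2 also requires the maximum, which would be 4.4 in every group. The case is therefore visible, though neither counted nor tied to a baseline category.

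**Step 4. Does any planned display count subjects by laboratory grade?**

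| Display | Shows magnitude? | Counts subjects by grade? |
|---|---|---|
| Shift tables (SAP 9.2) | No, only side of range | No |
| Descriptive change (SAP 5.2, 9.2) | Yes, including maximum | No |
| AE tables (SAP 9.1) | By severity | Yes, but only for results that became AEs |
| Listings (SAP 9.2) | Yes, with grade where available | No, by-subject only |

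Entry to the AE tables rests on clinical judgement. Under Protocol 10.1.2, abnormal findings that the investigator considers not clinically significant are generally not recorded as AEs, while changes needing treatment are. No planned table gives a grade count free of that judgement.

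**The case against.** The strongest reply is that nothing is concealed and little is lost. Protocol 11.1 allows the SAP to differ if it says where, and SAP 9.2 and 14 do so with a reason. The study is descriptive, and no decision rule uses the shift table. Protocol 11.4.1 names no laboratory endpoint, and exclusion criterion 5 makes marked baseline abnormality less likely. All of this stands and limits the weight of the point. It does not answer why grades are dropped where they exist.

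Three stronger readings are tempting and are not supported.

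- A reader might infer that an organ-toxicity signal could surface only as an unchanged category. Maximum change by visit and group, the listings and AE reporting of clinically significant results all contradict this. SAP 9.1 also counts Grade 2 or higher events other than cutaneous injection site reactions, which would include laboratory AEs.
- A reader might put a number on affected subjects by assuming a rate of abnormal baselines. The documents give neither that rate nor a rate of worsening. Such a product would only bound the subjects who could be affected; the number who worsen could be zero.
- A reader might blame the three categories for showing a small crossing of a limit as a shift. Any banded table does this at its cut-points, graded tables included.

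One further objection stands in part. The documents do not reproduce the CTCAE criteria, so which parameters can be graded cannot be settled from them. SAP 9.2 qualifies the range indicator as subject to availability, and Protocol 8.4.4 allows central or local laboratories. Derivability has to be checked parameter by parameter.

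**Conclusion.** The point holds as a limited one. The SAP's reason does not cover the scope of its change, and the resulting shift tables carry no information on magnitude beyond a limit, even for parameters with a grade. That follows from the categories alone and does not depend on the assumed limits or example values.

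The practical size is modest. A large worsening would remain visible elsewhere in the report. The loss is a count of subjects by laboratory toxicity grade that does not depend on an investigator first calling the result clinically significant. The number of subjects concerned cannot be estimated from the documents. The departure is declared, so this is a question of proportion and not an undisclosed inconsistency.

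The conclusion assumes that at least some parameters have a supplied or derivable grade. The SAP's own wording suggests this but does not establish it.

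**What to change.** In SAP 9.2, keep the Low/Normal/High tables. Add the protocol's table of baseline grade against post-baseline grade, separately for the high and low directions, for each chemistry and hematology parameter where a CTCAE v5.0 grade is supplied or can be derived from the result, the baseline value and the reference limits. State which parameters have no grade. Amend the entry in SAP 14 so that the departure is confined to those parameters.

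No new data are needed. The cost is SAP wording plus programming and validating the grade derivation for each parameter, including a check that reference limits are present for the values concerned.
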